10.1.4 Clinical Laboratory Changes

Changes in laboratory values, vital signs or other safety parameters (e. g., neurological and clinical symptom assessments) as noted in the protocol are a subset of AEs and are reportable only if the lab test result is associated with accompanying symptoms, and/ or requires additional diagnostic testing or intervention (medical, surgical), and/or requires additional significant treatment, and/or requires temporal or permanent discontinuation of study drug, or a change to dosing other than as permitted by protocol, or if considered to be clinically significant by Investigator or medically qualified designee.

Screening laboratory assessments, if determined to be clinically significant by the Investigator, are not AEs.

Confidential Page 58 of 108

11 SERIOUS ADVERSE EVENTS

The Investigator or designee is responsible for identifying, documenting and reporting events that meet the definition of an SAE.

An SAE is any event that meets any of the following criteria:

- Death
- Life threatening
- In-patient hospitalization or prolongation of existing hospitalization
- Persistent or significant disability/incapacity
- Congenital anomaly/birth defect in the offspring of a subject who received INDV-2000
- Other: Important medical events that may not result in death, be life threatening or require hospitalization, may be considered an SAE when, based upon appropriate medical judgment, they may jeopardize the subject and may require medical or surgical intervention to prevent one of the outcomes listed in this definition. Examples of such events are:
 - o Intensive treatment in an emergency room or at home for allergic bronchospasm
 - o Blood dyscrasias or convulsions that do not result in in-patient hospitalization
 - o Development of study drug abuse or diversion
- Potential Hy's Law cases indicative of medication-induced hepatocellular injury, defined as:
 - o ALT $\ge 3x$ ULN and total bilirubin of $\ge 2x$ ULN (or INR > 1.5 if measured)
 - o ALT or AST >3x ULN with systemic symptoms (fatigue, nausea, vomiting, right upper quadrant pain or tenderness, fever, rash and/or eosinophilia [>5%])
- Potential Hy's Law cases should be managed as described in Section 22.4, Appendix 4.

An AE is considered "life threatening" if the subject was at immediate risk of death from the event as it occurred; i.e., it does not include a reaction that if it had occurred in a more serious form might have caused death. For example, study drug-induced hepatitis that resolved without evidence of hepatic failure would not be considered life threatening even though study drug-induced hepatitis can be fatal.

AEs requiring hospitalization will be considered SAEs. Hospitalizations for elective surgery or routine clinical procedures that are not the result of an AE (e. g., elective surgery for a pre-existing condition that has not worsened) should not be considered AEs or SAEs. If anything untoward is reported during the procedure, that occurrence must be reported as an AE (either 'serious' or 'non-serious') according to the usual criteria.

In general, hospitalization signifies that the subject has been detained (usually involving at least an overnight stay) at the hospital or emergency ward for observation and/or treatment that would not have been appropriate in the physician's office or other outpatient setting. Complications that occur during hospitalization are AEs. If a complication prolongs hospitalization or fulfils any other serious criteria, the event is serious. When in doubt as to whether 'hospitalization' occurred or was necessary, the AE should be considered serious.

Confidential Page 59 of 108

An AE is incapacitating or disabling if the experience results in a substantial and/or permanent disruption of the subject's ability to carry out normal life functions.

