6.5.1.1 Part I and II - Individual Stopping Criteria

If the following criteria are met at any point during Parts I or II, the affected individual's dosing will be paused to allow unblinded review of affected individuals by the DRSC before continuing dosing. A healthy volunteer will be discontinued if any of the criteria listed below are confirmed:

AEs:

• The healthy volunteer experiences an SAE that is not clearly unrelated to the IMP.

Laboratory Abnormalities:

The healthy volunteer has an abnormality of one or both of the following parameters, whose temporal relationship to the IMP makes causality plausible, confirmed on repeat testing:

- Serum ALT or AST >3 times the ULN
- Total serum bilirubin >2 times the ULN (>35% direct bilirubin).

Vital Signs:

The healthy volunteer fulfils one or both of the following vital sign criteria based on the mean of triplicate measures (≥ 1 minute apart), that will be completed once the first blood pressure reading is outside the accepted range:

- Systolic blood pressure (SBP) <85 or >170 mmHg and/or change from Baseline >30 mmHg sustained for at least 1 hr (measures repeated every 15 min)
- Diastolic blood pressure (DBP) <45 or >105 mmHg and/or change from Baseline >30 mmHg sustained for at least 1 hr (measures repeated every 15 min)

ECG Criteria:

The healthy volunteer fulfils the following ECG criteria based on the mean of triplicate measures (≥ 1 minute apart), that will be completed once the first ECG demonstrates a prolonged interval:

• QTcF ≥500 msec or uncorrected QT interval of >600 msec.

Plasma INDV-2000 Concentrations

Confidential Page 35 of 108

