6.5.1.3 Part III - Individual Stopping Criteria

A subject will be discontinued if any of the criteria listed below are fulfilled:

AEs:

• The subject experiences an SAE that is not clearly unrelated to the IMP.

Laboratory Abnormalities:

The subject has an abnormality of one or both of the following parameters, whose temporal relationship to the IMP makes causality feasible, confirmed on repeat testing:

Confidential Page 36 of 108

- Serum ALT or AST >5 times the ULN or 2-fold above baseline if baseline is \geq 1.5 times ULN.
- Total serum bilirubin >2 times the ULN (>35% direct bilirubin).

ECG Criteria:

The subject fulfils the following ECG criteria based on the mean of triplicate measures (≥ 1 minute apart), completed once the first ECG demonstrates a prolonged interval:

• QTcF \ge 500 msec or uncorrected QT interval of >600 msec.

If the preceding criteria are met, the DRSC will conduct a review of the affected individuals to determine if any additional safety monitoring or changes to the protocol are required.

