6.5.1.4 Study Stopping Criteria (Parts I, II and III)

If the following criteria are met at any point during the study, the current cohort will be paused to allow review of the affected individuals by the DRSC before continuing dosing.

AEs:

- Four subjects experience a similar severe AE that is not clearly unrelated to the IMP, or
- Two subjects experience a similar SAE that is not clearly unrelated to the IMP.

Laboratory Abnormalities:

Two subjects with an abnormality of both of the following parameters, whose temporal relationship to the IMP makes causality feasible, confirmed on repeat testing:

- Serum ALT or AST >3 times the ULN or 2-fold above baseline if baseline is \ge 1.5 times ULN.
- Total serum bilirubin >2 times the ULN (>35% direct bilirubin).

ECG Criteria:

Three subjects fulfil the following ECG criteria based on the mean of triplicate measures (≥ 1 minute apart), that will be completed once the first ECG demonstrates a prolonged interval:

• QTcF \ge 500 msec or uncorrected QT interval of >600 msec.

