22.4 APPENDIX 4 – Liver Safety

The following must occur if a subject meets any of the liver chemistry stopping criteria as outlined in Section 6.5 of the protocol:

- Subject must immediately be withdrawn from treatment. Do not re-challenge with study treatment.
- Notify the Indivior Medical Monitor or specified designee within 24 hours of learning of the abnormality.
- Completed the "Safety Follow-up Procedures" listed below.
- Upon completion of the safety follow-up, the subject must be withdrawn from the study unless further follow-up is required.

Subjects with ALT $\ge 3x$ ULN and bilirubin $\ge 2x$ ULN (>35% direct); or ALT $\ge 3x$ ULN and INR >1.5:

This event is an SAE and must be reported using the SAE Reporting Form (Section 11). Serum bilirubin fractionation should be performed, if testing is available. If fractionation is unavailable, urinary bilirubin is to be measured via dipstick (a measurement of direct bilirubin, which would suggest liver injury).

Make every reasonable attempt to have the subject return to the clinic within 24 hours for repeat liver chemistries, additional testing and close monitoring (with specialist or hepatology consultation recommended).

Monitor the subject twice weekly until liver chemistries (ALT, AST, alkaline phosphatase, bilirubin) resolve, stabilize or return to within baseline values.

Subjects with ALT $\geq 5x$ ULN or ALT $\geq 3x$ ULN who have hepatitis symptoms or rash, cannot be monitored for 4 weeks or have elevations that persist ≥ 4 weeks:

- Make every reasonable attempt to have the subject return to the clinic within 24-72 hours for repeat liver chemistries and additional testing.
- Monitor subject weekly until liver chemistries (ALT, AST, alkaline phosphatase, bilirubin) resolve, stabilize or return to within baseline values.

Subjects with ALT ≥3x ULN and <5x ULN and bilirubin <2x ULN, who do not exhibit hepatitis symptoms or rash:

• Contact the Indivior Medical Monitor within 24 hours of learning of the abnormality to discuss subject safety.

- Subject may continue study treatment, if liver chemistries (ALT, AST, alkaline phosphatase, bilirubin) can be monitored weekly for up to 4 weeks.
- If the subject later meets the liver chemistry stopping criteria (outlined in Section 6.5 of the protocol), immediately withdraw study treatment, perform additional testing and continue safety follow-up until liver chemistries resolve, stabilize or return to baseline values.

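### The bilirubin/INR arm of the potential Hy's Law SAE names ALT only, so an asymptomatic AST-driven case with raised bilirubin is not automatically an SAE

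*Protocol*

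**What the plan says.** Protocol Section 11 defines potential Hy's Law cases by two arms and lists them among SAEs. The bilirubin/INR arm is "ALT $\ge 3x$ ULN and total bilirubin of $\ge 2x$ ULN (or INR > 1.5 if measured". The second arm is "ALT or AST >3x ULN with systemic symptoms". AST therefore appears only where symptoms are present.

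The transaminase limits in Section 6.5 name either enzyme:

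- 6.5.1.1 (individual, Parts I and II): "Serum ALT or AST >3 times the ULN". The cohort rule in 6.5.1.2 uses the same limit.
- 6.5.1.3 (individual, Part III): "Serum ALT or AST >5 times the ULN or 2-fold above baseline", the second alternative applying when baseline is at least 1.5x ULN.
- 6.5.1.4 (study level, all parts): "Serum ALT or AST >3 times the ULN or 2-fold above baseline", with the same baseline condition. Two subjects must each have the transaminase and the bilirubin abnormality.

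The bilirubin limits in Section 6.5 require more than 35% direct bilirubin. The Section 11 arm has no such condition.

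Appendix 4 (Section 22.4) has a category for ALT with bilirubin (more than 35% direct) or ALT with INR, and says of it "This event is an SAE and must be reported using the SAE Reporting Form (Section 11". Its other follow-up categories are also set by ALT.

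Section 11 keeps a general route: an important medical event "may be considered an SAE when, based upon appropriate medical judgment".

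**The concern.** The protocol treats AST and ALT as equivalent when it decides whether to stop a subject or pause a cohort. It does not do so when it decides whether transaminase plus bilirubin is an SAE. No reason for the difference appears in the visible text.

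TESAEs are a primary endpoint (Protocol 14.7.1; SAP 5.3.1 for Part III). SAE status also brings the SAE form, the notice to Pharmacovigilance and the SUSAR assessment (Protocol 11.2.1 and 11.2.2), and it feeds the SAE clauses of the stopping rules. The visible laboratory text in SAP 5.5.3.1 plans values, changes and normal/abnormal shifts by visit, with no joint transaminase-bilirubin summary. The SAE definition is thus the main visible route by which the joint signal would be tabulated.

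**Working it through.** The plan gives no figure to reproduce; the study is descriptive (SAP Section 2). The check applies the written rules to illustrative profiles.

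**Assumptions, not taken from the documents:** the laboratory values (multiples of ULN); onset after first IMP; baseline ALT and AST below 1.5x ULN; results confirmed on repeat with a plausible causal link, as Section 6.5 requires; INR not measured; no other seriousness criterion met.

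**Rules applied**

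- Section 11 SAE: (ALT ≥3 and bilirubin ≥2), or (ALT or AST >3 with symptoms).
- Appendix 4 SAE category: ALT ≥3, bilirubin ≥2 and direct >35%.
- Individual laboratory limit, Parts I/II: ALT or AST >3, or bilirubin >2 with direct >35%.
- Individual laboratory limit, Part III: ALT or AST >5, or bilirubin >2 with direct >35%.
- Study-level laboratory clause: ALT or AST >3, and bilirubin >2 with direct >35%.

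| Profile | ALT | AST | Bilirubin | Direct >35% | Symptoms | Section 11 Hy's Law SAE | App. 4 SAE | Limit I/II | Limit III | Counts in 6.5.1.4 |
|---|---|---|---|---|---|---|---|---|---|---|
| A | 4 | 4 | 2.5 | yes | no | yes | yes | yes | yes | yes |
| B | 2 | 4 | 2.5 | yes | no | **no** | no | yes | yes | yes |
| C | 2 | 4 | 2.5 | yes | yes | yes | no | yes | yes | yes |
| D | 2 | 6 | 2.5 | yes | no | **no** | no | yes | yes | yes |
| E | 2 | 4 | 2.5 | no | no | **no** | no | yes | **no** | **no** |
| F | 4 | 2 | 2.5 | no | no | yes | no | yes | no | no |

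**Reading the table**

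1. A and B differ only in ALT. A is an automatic SAE and B is not, although both meet the individual limits and count towards the study-level clause. B meets the Part III limit through bilirubin, since its AST is below 5x.
2. D exceeds both the transaminase and the bilirubin limit in Parts I/II and in Part III, yet meets neither Section 11 arm.
3. E and F exchange the enzymes. F is an automatic SAE because 4 ≥ 3 and 2.5 ≥ 2 and Section 11 sets no direct-fraction condition. If not clearly unrelated to IMP, F then meets the SAE criterion in 6.5.1.3, and two similar cases meet the SAE clause in 6.5.1.4. In Part III, E meets no automatic rule at all, and the Appendix 4 lead-in does not apply because no Section 6.5 liver criterion is met. Whether E is even a reportable AE turns on the conditions in 10.1.4.
4. If the bilirubin/INR arm named either enzyme, B, D and E would change from no to yes in the Section 11 column. Nothing else in the table would change.

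**Size of one classification:** in Part III at full enrolment, 1/16 = 6.25%, or 6.3%. In a Part I/II active cohort, 1/9 = 11.1%. These show the effect of one such case; the documents give no expected frequency.

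**The case against.** A reader might infer that an AST-driven case cannot be an SAE, drops out of the primary endpoint, or escapes the pause rules. The documents do not support this.

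- **SAE status.** The important-medical-event clause and the other criteria, such as hospitalization, remain open. What is missing is automatic classification. A reported TESAE incidence of 0% would follow only if no other route were used.
- **Primary endpoint.** A laboratory change that requires discontinuation is a reportable AE (10.1.4), and TEAEs leading to discontinuation are themselves primary (Protocol 14.7.1; SAP 5.3.1). Profiles B and D would move between components of the endpoint.
- **Notification and follow-up.** For anyone meeting a Section 6.5 liver criterion, AST included, Appendix 4 requires withdrawal from treatment, notice to the Medical Monitor within 24 hours and a set of follow-up tests. Only the ALT-tiered visit frequency and the mandatory SAE report are left unassigned.
- **Pause rules.** Two subjects like B or D already meet the laboratory clause in 6.5.1.2 within a cohort, and that in 6.5.1.4. In Parts I/II a single one pauses that subject's dosing for DRSC review.
- **Purpose and rarity.** Stopping limits and SAE definitions need not match, and AST can rise from sources other than the liver. The profile is also narrow: any one of the listed systemic symptoms makes it an SAE.

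These points stand and limit the concern. They do not explain why the two arms of one definition name different enzymes. The first four give no automatic protection to profile E in Part III, where no Section 6.5 limit is met.

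**Conclusion.** The inconsistency is real and its effect is limited. For an asymptomatic case with AST above 3x ULN, ALT below 3x ULN and bilirubin at or above 2x ULN, TESAE status and mandatory SAE reporting rest on judgment or another seriousness criterion. For the ALT equivalent they are automatic.

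In Parts I/II this is a matter of classification and reporting, because AST above 3x ULN meets the individual limit on its own, given confirmation and plausible causality. In Part III there is also a gap in the automatic rules. It holds for AST between 3x and 5x ULN, direct bilirubin at most 35%, no symptoms and, so that the 2-fold clause cannot apply, baseline AST below 1.5x ULN.

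One case moves TESAE incidence by 6.3 percentage points in Part III with 16 subjects. No sample size, power or error rate is affected. This is an inexpensive improvement to safety capture and does not put the primary analysis in doubt.

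**What to change.** In the Section 11 SAE reporting definition, have the bilirubin/INR arm name the same enzymes as the symptom arm and Section 6.5, or state why AST is deliberately excluded.

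The wording change is a few words in an amendment. The cost is that an occasional AST rise of non-hepatic origin with coincident raised bilirubin will be reported as an SAE and then assessed for cause. The sponsor should note the knock-on effects: Section 11 sends potential Hy's Law cases to Appendix 4, and SAE status feeds the SAE criteria in Section 6.5.

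For that reason the ALT-only categories in Appendix 4 must be reconciled with Sections 6.5 and 11. So must the direct-bilirubin conditions, which are present in Section 6.5 and in the Appendix 4 SAE category but absent from Section 11. How to do so is for the sponsor; no monitoring or stopping rule is proposed here.

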11.1 Documenting Serious Adverse Events

When an SAE occurs, it is the responsibility of the Investigator to review all documentation (e.g., hospital progress notes, laboratory and diagnostic reports) pertaining to the event. The Investigator will then record all relevant information regarding the SAE on the appropriate electronic or paper form(s).

It is not acceptable for the Investigator to send photocopies of the subject's medical records to Indivior in lieu of completion of the SAE Reporting Form. However, there may be cases where copies of medical records are requested by Indivior or designated representative. In this instance, all subject identifiers, with the exception of subject number, will be redacted on the copies of the medical records prior to submission to Indivior.

The Investigator will attempt to establish a diagnosis of the event based on signs, symptoms and/or other clinical information. In such cases, the diagnosis will be documented as an AE or SAE and not the individual signs/symptoms.

Additional PK samples may be collected for subjects who experience an SAE. Samples should be collected as soon as the Investigator is made aware of the SAE and additional blood samples may be collected after resolution of the SAE.

11.2 Reporting Serious Adverse Events

11.2.1 Investigator Reporting of Serious Adverse Events

Once the Investigator determines that an event meets the protocol definition of an SAE, the SAE will be reported to Indivior (or designated representative) by the Investigator (or designee) within 24 hours from first being aware of the event using the form provided by Indivior or designated representative. Any follow-up information on a previously reported SAE will also be reported to Indivior within 24 hours.

Where additional information is needed or expected, the Investigator will not wait to receive all information before reporting the event to Indivior. The Investigator must provide an assessment of causality at the time of the initial report as described in Section 10.1.3.

In the event of an SAE, the Investigator or designee will notify both the Indivior Medical Monitor at the phone number and/or email address listed under Study Personnel Information and Indivior Pharmacovigilance by completing the appropriate form(s). A paper SAE Reporting Form must be completed and submitted to Indivior Pharmacovigilance:

Confidential Page 60 of 108

11.2.2 Regulatory Reporting Requirements for Serious Adverse Events

Prompt receipt of notifications of SAEs to Indivior or designated representative from Investigators is essential in ensuring that legal obligations and ethical responsibilities regarding the safety of subjects are met.

Indivior has a legal responsibility to notify both the local regulatory authority and other regulatory agencies about the safety of the IMP. Indivior or designated representative will comply with country-specific regulatory requirements pertaining to safety reporting to Regulatory Authorities, IRBs and Investigators.

A suspected unexpected serious adverse reaction (SUSAR) is an SAE related to the IMP administered in any dose and that, in its nature or severity, is inconsistent with the IB. Indivior Pharmacovigilance will determine if an SAE meets the definition of a SUSAR and distribute SUSAR reports according to local regulatory requirements and Indivior policy. An Investigator who receives an Investigator safety report describing an SAE or other specific safety information (e.g., summary or line listing of SAEs, Dear Investigator Letter) will file it with the IB and will notify the IRB, if required according to local requirements.

11.2.3 Overdose

Any instance of overdose with concomitant medications or illicit drugs must be communicated as an SAE and fully documented. Any symptoms of overdose with study drug would be assessed according to criteria for treatment-emergent and SAEs outlined in sections above. Details of any signs or symptoms and their management should be recorded, including details of any antidote(s) administered.

Confidential Page 61 of 108

12 PREGNANCY

In the case where a subject's routine pregnancy test as required per protocol is positive for pregnancy prior to dosing, the subject must not be dosed. If the subject has a positive urine pregnancy test, a confirmatory serum pregnancy test will be performed.

12.1 Action to be Taken if Pregnancy Occurs in a Female Subject

If a female subject suspects that she is pregnant (e.g., missed period, self-administered pregnancy test) during treatment or within 90 days of the last exposure to study drug, treatment will be immediately stopped, where applicable. The subject will be instructed to return to the clinical unit as soon as possible (preferably within 48 hours) to undergo a serum pregnancy test. If the result of the serum pregnancy test confirms the subject is pregnant, the subject will be discontinued from the study and will undergo all final study visit procedures (with the exception of any additional pregnancy testing).

In the case where a subject's routine pregnancy test as required per protocol is positive for pregnancy, treatment will be immediately stopped. If the subject has a positive urine pregnancy test, a confirmatory serum pregnancy test should be performed. The subject will be discontinued from the study and complete final study visit procedures (with the exception of any additional pregnancy testing). The Investigator should fully inform the female subject of the serious risk to the foetus as well as discuss the desirability of continuing the pregnancy.

The Investigator will record pregnancy information on the appropriate form and submit it to Indivior or designated representative within 24 hours of learning of the pregnancy. The subject will also be followed to determine the outcome of the pregnancy and information on the status of the mother and child will be forwarded to Indivior or designated representative. Generally, follow-up will be no longer than 6 to 8 weeks following the estimated delivery date. Any premature termination of the pregnancy will be reported regardless of foetal status (presence or absence of anomalies) or indication for procedure.

